GDPR	General Data Protection Regulation
ICF	Informed Consent Form
ID	Identification
IFU	Indications for Use
ISO	International Standards Organization
MDCG	Medical Device Coordination Group
MDR	Medical Device Regulation
MEDDEV	Medical Device Directive
OP	Operative
PI	Principal Investigator
PMCF	Post-Market Clinical Follow-Up
PMSP	Post Market Surveillance Plan
Post-OP	Post-operative
PROM	Patient-Reported Outcome Measures
SADE	Serious Adverse Device Effect

SAE	Serious Adverse Event
SS	Study Subject
UADE	Unanticipated Adverse Device Effect
USADE	Unanticipated Serious Adverse Device Effect

4 Study Synopsis

Complete Protocol Title	Post-market Clinical Follow-up Study to Provide Safety, Performance and Clinical Benefits Data of the Zimmer® Reconstruction System (Implant and Instrumentation) – A Retrospective Consecutive Series Study
Protocol Number	MDRG2017-89MS-99T
Short Protocol Title	Zimmer Reconstruction System
Sponsor	Zimmer GmbH, Zug, Switzerland
Manufacturer	Zimmer Inc.
Study Device(s)	
Zimmer Reconstruction System and respective instrumentation
  
Straight Reconstruction Plate
  
Curved Reconstruction Plate
  
Symphyseal B ridge plate
  
Cortical screw

Technical Documentation Reference Number	401, 402a, 402s, 425b, 850
Study Objectives/Endpoints	The objective of this retrospective post-market clinical follow-up (PMCF) study is to collect data confirming safety, performance and clinical benefits of the Zimmer Reconstruction System (implants and instrumentation) when used for temporary internal fixation and

	
stabilization of fractures during the normal healing process.
 
The primary objective is the assessment of performance by analyzing fracture healing.
 
The secondary objectives are the assessment of safety by recording and analyzing the incidence and frequency of complications and adverse events. Relation of the events to implant, instrumentation and/or procedure should be specified. Subjects' outcomes will also be assessed.

Indications/Target Population	
Consecutive series of cases implanted with the Zimmer Reconstruction System according to the indications for use. Inclusion/exclusion criteria are in accordance with the indications and contraindications in the Instruction For Use (IFU).

Inclusion/Exclusion Criteria	
Inclusion Criteria:
 
Patients having received the Zimmer Reconstruction System for temporary internal fixation and stabilization of fractures during the normal healing process.
 
Exclusion Criteria:
 
 • Off-label use • Patients under the age of 18 • Severely comminuted fractures in which bone fragments are too small or numerous to adequately fix or maintain a reduced position. • Infection. • Metal sensitivity or intolerance. • Severe osteopenia and/or osteoporosis, or in the presence of marked or rapid bone absorption, metabolic bone disease, cancer, or any other tumor-like condition of the bone which may compromise fixation. • Sternal or spinal fractures. • Anatomical location in which the device would interfere with nerves, blood vessels, or other vital structures.

	
 Patients with inadequate soft tissue coverage at the implant site.
Study Design	Single-Center, Retrospective, Non-controlled, Non-randomized, Consecutive series
Clinical Phase	Post-market
Sample Size	The goal is to collect data on a total of 83 consecutive cases operated with the the Straight Reconstruction Plate, Curved Reconstruction Plate and/or Symphyseal Bridge Plate, aiming for an equal number of each.
Length of Study	
12 months overall:
 
 Ethics Committee approval Identify and enroll subjects into the study Collection of baseline and follow-up (FUP) information available in medical notes from the pre-operative condition to the immediate post-op and last consultation visit Conduct data collection and analysis Write the final report
Materials and Methods	Retrospective data will be collected from medical charts including baseline information from the preoperative, operative, immediate post-operative interval and last consultation visit. Zimmer Biomet will receive only an anonymized report.
Data Collection	Paper/Electronic
Statistical Reporting	Statistical Analysis will be conducted by the Azienda Ospedaliero Universitaria Senese, Siena, Italy.
Scores/Performance Assessments	Harris Hip Score (HHS), Fracture Healing, Adverse Events
Standards	
The PMCF is compliant with the below:
 
 ISO 14155: 2020 - Clinical investigation of medical devices for human subjects - Good clinical practice [1]. The Declaration of Helsinki (DoH) - Ethical principles for medical research involving human subjects [2]. European Regulation (EU) 2017/745 [3]. MDCG 2020-10/1 Safety reporting in clinical investigations for medical devices under the

	Regulation (EU) 2017/74 [4]
Study Funding	Funding for this clinical study is made available by Zimmer Biomet to support clinical data collection, EC review fees and other expenses associated with the conduct and execution of this study protocol as outlined in the fully executed Clinical Trial Agreement.

5 Data Collection Overview

The following information and data will be collected on all cases:

Evaluation	Baseline			Last Consultation Visit (min. 1 year post-op)
	Prior to Surgery	Surgical/Operative	Immediate Post-Operative	
Inclusion/Exclusion Criteria	PI			
Demographic Evaluation	PI			
Physical Exam			PI	
Operative Information/ Surgical Device Information		PI		
Immediate Post-Operative Evaluation			PI	
Harris Hip Score [5].				PI
Fracture Healing (including x-rays and/or clinically)				PI
Protocol Deviation		If required		
Complications/Adverse Events (AE relation or not to device, instrumentation and/or procedure)				

PI: completed by Principal Investigator or qualified designee

6 Introduction and Purpose

Falls and motor vehicle accidents, the two most common mechanisms of traumatic injury [4, 5], sometimes result in fractures or other disruptions of the pelvic ring. Fractures following high-energy trauma are often associated with extensive soft tissue injuries. The state of the surrounding soft tissues and the local blood supply to the bone are the most important factors determining the tendency of the fracture to heal [6-12]. In high-energy pelvic trauma [fractures](#), temporary fixation with plates is indicated to stabilize the pelvic ring in order to control hemorrhage, creates high stability and reduces motion in the joint or at the fracture site.

The Zimmer Reconstruction System is a CE marked and FDA cleared implant system that has been in clinical use since 1995. The purpose of this retrospective PMCF study is to confirm safety, performance and clinical benefits of the Zimmer Reconstruction System when used for temporary internal fixation and stabilization of fractures during the normal healing process.

7 Study Device Information

7.1 Study Device

The Zimmer Reconstruction System is designed to provide temporary fixation of fractures primarily in the pelvic region. The implant system is comprised of straight, curved, and symphyseal bridge reconstruction plates and screws used to fix the plates to the fractured bones. The plates, screws and spherical washers that are manufactured from 316L stainless steel and are provided in a range of sizes and lengths to accommodate patient size and skeletal morphology. Representative illustrations of each implant type, screws and ancillary components appear in Figures 1 (1a through 1e).

[figure not shown]

Figure 1: Zimmer Reconstruction System implants, screws and ancillary components

The plates are malleable so they can be precisely contoured to the appropriate shape using plate bending instrumentation as shown in **Figure 2**.

Figure 2: Bending Pliers Holding a Curved Reconstruction Plate

The plates are available in non-sterile and sterile versions and can accommodate bone screws.

7.2 Device Scope

For simplicity purposes, only the plates and washers are listed in the scope below, however the study aims to collect data on all implants and instruments (incl. ancillary components) of the Zimmer Reconstruction System.

Part Number Sterile	Part Number Unsterile	Item description
00-1179-002-02	47-1179-002-02	ZIMMER RECONSTRUCTION SYSTEM SYMPHYSEAL BRIDGE PLATE 4 HOLES LARGE
00-1179-002-04	47-1179-002-04	ZIMMER RECONSTRUCTION SYSTEM SYMPHYSEAL BRIDGE PLATE 4 HOLES SMALL
00-1179-005-03	47-1179-005-03	ZIMMER RECONSTRUCTION SYSTEM 3.5 MM RECON BONE PLATE - STRAIGHT 3 HOLES
00-1179-005-04	47-1179-005-04	ZIMMER RECONSTRUCTION SYSTEM 3.5 MM RECON BONE PLATE - STRAIGHT 4 HOLES
00-1179-005-05	47-1179-005-05	ZIMMER RECONSTRUCTION SYSTEM 3.5 MM RECON BONE PLATE - STRAIGHT 5 HOLES
00-1179-005-06	47-1179-005-06	ZIMMER RECONSTRUCTION SYSTEM 3.5 MM RECON BONE PLATE - STRAIGHT 6 HOLES
00-1179-005-07	47-1179-005-07	ZIMMER RECONSTRUCTION SYSTEM 3.5 MM RECON BONE PLATE - STRAIGHT 7 HOLES
00-1179-005-08	47-1179-005-08	ZIMMER RECONSTRUCTION SYSTEM 3.5 MM RECON BONE PLATE - STRAIGHT 8 HOLES
00-1179-005-09	47-1179-005-09	ZIMMER RECONSTRUCTION SYSTEM 3.5 MM RECON BONE PLATE - STRAIGHT 9 HOLES
00-1179-005-10	47-1179-005-10	ZIMMER RECONSTRUCTION SYSTEM 3.5 MM RECON BONE PLATE - STRAIGHT 10 HOLES
00-1179-005-11	47-1179-005-11	ZIMMER RECONSTRUCTION SYSTEM 3.5 MM RECON BONE PLATE - STRAIGHT, 11 HOLES
00-1179-005-12	47-1179-005-12	ZIMMER RECONSTRUCTION SYSTEM 3.5 MM RECON BONE PLATE - STRAIGHT 12 HOLES
00-1179-005-13	47-1179-005-13	ZIMMER RECONSTRUCTION SYSTEM 3.5 MM RECON BONE PLATE - STRAIGHT, 13 HOLES

00-1179-005-14	47-1179-005-14	ZIMMER RECONSTRUCTION SYSTEM 3.5 MM RECON BONE PLATE - STRAIGHT 14 HOLES
00-1179-005-15	47-1179-005-15	ZIMMER RECONSTRUCTION SYSTEM 3.5 MM RECON BONE PLATE - STRAIGHT, 15 HOLES
00-1179-005-16	47-1179-005-16	ZIMMER RECONSTRUCTION SYSTEM 3.5 MM RECON BONE PLATE - STRAIGHT 16 HOLES
00-1179-005-18	47-1179-005-18	ZIMMER RECONSTRUCTION SYSTEM 3.5 MM RECON BONE PLATE - STRAIGHT 18 HOLES
00-1179-005-20	47-1179-005-20	ZIMMER RECONSTRUCTION SYSTEM 3.5 MM RECON BONE PLATE - STRAIGHT, 20 HOLES
00-1179-005-22	47-1179-005-22	ZIMMER RECONSTRUCTION SYSTEM 3.5 MM RECON BONE PLATE- STRAIGHT, 22 HOLES
00-1179-006-06	47-1179-006-06	ZIMMER RECONSTRUCTION SYSTEM 3.5 MM RECON BONE PLATE - CURVED 6 HOLES
00-1179-006-08	47-1179-006-08	ZIMMER RECONSTRUCTION SYSTEM 3.5 MM RECON BONE PLATE - CURVED 8 HOLES
00-1179-006-10	47-1179-006-10	ZIMMER RECONSTRUCTION SYSTEM 3.5 MM RECON BONE PLATE - CURVED 10 HOLES
00-1179-006-12	47-1179-006-12	ZIMMER RECONSTRUCTION SYSTEM 3.5 MM RECON BONE PLATE - CURVED 12 HOLES
00-1179-006-14	47-1179-006-14	ZIMMER RECONSTRUCTION SYSTEM 3.5 MM RECON BONE PLATE - CURVED 14 HOLES
00-1179-006-16	47-1179-006-16	ZIMMER RECONSTRUCTION SYSTEM 3.5 MM RECON BONE PLATE - CURVED 16 HOLES
00-1179-006-18	47-1179-006-18	ZIMMER RECONSTRUCTION SYSTEM 3.5 MM RECON BONE PLATE - CURVED 18 HOLES
00-1179-006-20	47-1179-006-20	ZIMMER RECONSTRUCTION SYSTEM 3.5 MM RECON BONE PLATE - CURVED, 20 HOLES
00-1179-006-22	47-1179-006-22	ZIMMER RECONSTRUCTION SYSTEM 3.5 MM RECON BONE PLATE - CURVED, 22 HOLES
00-1179-006-24	47-1179-006-24	ZIMMER RECONSTRUCTION SYSTEM 3.5 MM RECON BONE PLATE - CURVED, 24 HOLES
00-1179-007-02	47-1179-007-02	ZIMMER RECONSTRUCTION SYSTEM 4.5 MM STRAIGHT RECON PLATE 2 HOLES
00-1179-007-03	47-1179-007-03	ZIMMER RECONSTRUCTION SYSTEM 4.5 MM STRAIGHT RECON PLATE 3 HOLES
00-1179-007-04	47-1179-007-04	ZIMMER RECONSTRUCTION SYSTEM 4.5 MM STRAIGHT RECON PLATE 4 HOLES
00-1179-007-05	47-1179-007-05	ZIMMER RECONSTRUCTION SYSTEM 4.5 MM STRAIGHT RECON PLATE 5 HOLES
00-1179-007-06	47-1179-007-06	ZIMMER RECONSTRUCTION SYSTEM 4.5 MM STRAIGHT RECON PLATE 6 HOLES
00-1179-007-07	47-1179-007-07	ZIMMER RECONSTRUCTION SYSTEM 4.5 MM STRAIGHT RECON PLATE 7 HOLES
00-1179-007-08	47-1179-007-08	ZIMMER RECONSTRUCTION SYSTEM 4.5 MM STRAIGHT RECON PLATE 8 HOLES
00-1179-007-09	47-1179-007-09	ZIMMER RECONSTRUCTION SYSTEM 4.5 MM STRAIGHT RECON PLATE 9 HOLES
00-1179-007-10	47-1179-007-10	ZIMMER RECONSTRUCTION SYSTEM 4.5 MM STRAIGHT RECON PLATE 10 HOLES
00-1179-007-11	47-1179-007-11	ZIMMER RECONSTRUCTION SYSTEM 4.5 MM STRAIGHT RECON PLATE 11 HOLES
00-1179-007-12	47-1179-007-12	ZIMMER RECONSTRUCTION SYSTEM 4.5 MM STRAIGHT RECON PLATE 12 HOLES
00-1179-007-13	47-1179-007-13	ZIMMER RECONSTRUCTION SYSTEM 4.5 MM STRAIGHT RECON PLATE 13 HOLES
00-1179-007-14	47-1179-007-14	ZIMMER RECONSTRUCTION SYSTEM 4.5 MM STRAIGHT RECON PLATE 14 HOLES
00-1179-007-15	47-1179-007-15	ZIMMER RECONSTRUCTION SYSTEM 4.5 MM STRAIGHT RECON PLATE 15 HOLES
00-1179-007-16	47-1179-007-16	ZIMMER RECONSTRUCTION SYSTEM 4.5 MM STRAIGHT RECON PLATE 16 HOLES
00-1179-013-06	47-1179-013-06	ZIMMER RECONSTRUCTION SYSTEM 2.7 MM STRAIGHT RECON PLATE 6 HOLES
00-1179-013-08	47-1179-013-08	ZIMMER RECONSTRUCTION SYSTEM 2.7 MM STRAIGHT RECON PLATE 8 HOLES
00-1179-013-10	47-1179-013-10	ZIMMER RECONSTRUCTION SYSTEM 2.7 MM STRAIGHT RECON PLATE 10 HOLES
00-1179-013-12	47-1179-013-12	ZIMMER RECONSTRUCTION SYSTEM 2.7 MM STRAIGHT RECON PLATE 12 HOLES
00-1179-013-14	47-1179-013-14	ZIMMER RECONSTRUCTION SYSTEM 2.7 MM STRAIGHT RECON PLATE 14 HOLES
00-1179-013-16	47-1179-013-16	ZIMMER RECONSTRUCTION SYSTEM 2.7 MM STRAIGHT RECON PLATE 16 HOLES
00-1179-013-18	47-1179-013-18	ZIMMER RECONSTRUCTION SYSTEM 2.7 MM STRAIGHT RECON PLATE, 18 HOLES
00-1179-013-20	47-1179-013-20	ZIMMER RECONSTRUCTION SYSTEM 2.7 MM STRAIGHT RECON PLATE, 20 HOLES

00-1179-013-22	47-1179-013-22	ZIMMER RECONSTRUCTION SYSTEM 2.7 MM STRAIGHT RECON PLATE, 22 HOLES
00-1179-013-24	47-1179-013-24	ZIMMER RECONSTRUCTION SYSTEM 2.7 MM STRAIGHT RECON PLATE, 24 HOLES

Table 1. Device Scope of the Zimmer Reconstruction System Implants

7.3 Instrumentation

The instruments are made of stainless steel. Some instruments, such as screwdrivers, have plastic handles. Implant and instrument cases store the plates and associated instrumentation and house them during sterilization.

[figure not shown]

Figure 3: Pelvic Reconstruction Instrument Set

[figure not shown]

Figure 4: Pelvic Reconstruction Clamp Set

7.4 Ancillary devices

The Spherical washers are used to increase screw head size and fit flush, for fracture fixation optimizing the compression and minimize intrusion of the screw head through the bone during screw insertion (see table 2).

Part number	Item description
00-1179-012-00	ZIMMER RECONSTRUCTION SYSTEM SPHERICAL WASHER FOR USE WITH 3.5 MM SCREW

Table 2. Zimmer Reconstruction System ancillary components

7.5 Compatibility

To determine whether devices have been authorized for use in a proposed combination with Zimmer and/or Biomet products, please contact your sales representative or visit the Zimmer Electronic Labeling Service (eLabeling) website: <https://labeling.zimmerbiomet.com/>.

7.6 Accountability of devices

Device accountability is not required for this study. The devices used in the study are commercially available via CE 515162.

8 Study Population

The study population will be comprised of a consecutive series of cases implanted with the Zimmer Reconstruction System according to Zimmer Biomet's IFU and meeting the inclusion criteria and none of the exclusion criteria of this study. Inclusion/exclusion criteria are based on the indications and contraindications in the IFU. See below inclusion and exclusion criteria to be considered to determine patient's eligibility.

8.1 Inclusion Criteria

Patients having received the Zimmer Reconstruction System for temporary internal fixation and stabilization of fractures during the normal healing process.

8.2 Exclusion Criteria

The exclusion criteria are:

- Off-label use
- Patients under the age of 18
- Severely comminuted fractures in which bone fragments are too small or numerous to adequately fix or maintain a reduced position
- Infection
- Metal sensitivity or intolerance
- Severe osteopenia and/or osteoporosis, or in the presence of marked or rapid bone absorption, metabolic bone disease, cancer, or any other tumor-like condition of the

bone which may compromise fixation

- Sternal or spinal fractures
- Anatomical location in which the device would interfere with nerves, blood vessels, or other vital structures
- Patients with inadequate soft tissue coverage at the implant site.

9 Study Objectives

This is a PMCF study to fulfil the post-market surveillance obligations according to Medical Device Directive, MEDDEV 2.12-2 and the Medical Devices Regulation (MDR 2017/745). The objective of this retrospective PMCF study is to collect data confirming safety, performance and clinical benefits of the Zimmer Reconstruction System (implant and instrumentation) when used for temporary internal fixation and stabilization of fractures during the normal healing process.

- Performance will be evaluated by assessing bone union radiographically and/or clinically
- Safety will be evaluated by monitoring the frequency and incidence of adverse events (AE), serious adverse events (SAE), adverse device effects (ADE), serious adverse device effects (SADE), unanticipated serious adverse device effects (USADE) and device deficiencies (DD). Relation of the events to implant, instrumentation and/or procedure should be specified.
- Clinical benefits will be determined by the Harris Hip Score recorded at the longest follow-up after surgery (at least 1 year post-operative).

10 Study Design and Endpoints

10.1 Disease/Condition Being Treated

In this study the Zimmer Reconstruction system is used to stabilize fractures through temporary internal fixation during the normal healing process.

10.2 Number of Sites and Regions

This is a monocentric study performed at the Hospital Azienda Ospedaliero Universitaria Senese in Siena, Italy.

10.3 Number of Cases and Maximum Enrollment per Investigation Site

The goal is to collect data on a total of 83 consecutive cases operated with the Straight Reconstruction Plates, Curved Reconstruction Plates and/or Symphyseal Bridge Plates defined in the device scope

section of this protocol, aiming for an equal number of each.

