10.5 Study Design

This is a monocentric, retrospective and consecutive series post-market clinical study. Consecutive series of cases implanted with the Zimmer Reconstruction System between 2010 and 2018 at the Hospital Azienda Ospedaliero Universitaria Senese in Siena, Italy will be identified and included in the study. The consecutive cases will be enrolled in the reverse chronological order that they were operated. This means enrollment will start with patients operated in 2018 and consecutively going backwards towards 2010 until the necessary number of cases has been reached.

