10.7 Type and Timing of Observations

This study is designed to be retrospective. To avoid bias, consecutive series of cases will be identified and included in the study. The study duration is expected to be 12 months overall, which corresponds to time dedicated to the retrospective data collection from hospital charts from the pre-operative condition to the last consultation visit (at least 1-year post-operative), to conduct the analysis and to draft the final report.

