11.1 Study Participation

Each consecutive case implanted with the Zimmer Reconstruction System for temporary internal fixation and stabilization of fractures during the normal healing process between 2010 and 2018 at the Hospital Azienda Ospedaliero Universitaria Senese in Siena, Italy will be identified and included in the study until the required sample size of 83 cases is reached.

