11.4.2 Subject Identification Log

The site shall maintain a log of all subjects included in the clinical investigation, assigning an identification code linked to their names, alternative subject identification or contact information. All patients who meet the inclusion criteria and none of the exclusion criteria must be entered on the log sequentially. If a subject receives multiple implants, a dataset will be recorded per fractured site. Each case, i.e. fractured site, will have a different identification code. A Subject Identification Log must be maintained throughout the study and is included in the Investigator Binder. This list is kept in a safe place in the hospital.

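### The aim of equal numbers of three plate types conflicts with strictly consecutive enrolment, and the plan does not say which instruction prevails

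*Combined protocol and SAP*

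**What the plan says.** Section 10.3 sets the target in one sentence. It begins "The goal is to collect data on a total of 83 consecutive cases operated with" the three plate types, joined by and/or, and ends "aiming for an equal number of each". The Sample Size row of the synopsis repeats this ("Symphyseal Bridge Plate, aiming for an equal number of each").

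The enrolment rules take no account of plate type:

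- Section 10.5: "The consecutive cases will be enrolled in the reverse chronological order that they were operated". It adds that "enrollment will start with patients operated in 2018 and consecutively going backwards towards 2010 until the necessary number of cases has been reached".
- Section 11.1: each consecutive case from 2010 to 2018 "will be identified and included in the study until the required sample size of 83 cases is reached".
- Sections 8.1, 8.2 and 11.5: eligibility does not depend on which plate was used.
- Section 10.7 gives the reason for the design: "To avoid bias, consecutive series of cases will be identified and included in the study".

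Section 16.1 tests one pooled healing rate, with no plate strata or weights. Section 16.2 allows subgroup summaries as needed but does not name plate type.

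**The concern.** A consecutive series takes whatever plate mix the hospital used. An equal split can be steered towards only by leaving out eligible cases with the commoner plates and reaching further back for the rarer one. The plan contains both instructions and neither ranks them nor says how a site should act when they diverge. It also has no rule for counting a case that carries two plate types, which the and/or wording allows.

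At stake is the safeguard named in section 10.7. The study has no control group. Healing is already recorded in the charts, the investigator reviews the radiographs (11.11), and the investigator's team manages the data (12.2.5). A balance aim without a rule gives people who can see the outcome a protocol-based reason to leave a case out. Nothing in the documents suggests that this would be done by outcome. The purpose of a consecutive series is that the question cannot arise.

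**Working it through.** **1. The plan's own figure.** From section 16.1: null rate 0.90 − 0.10 = 0.80, expected rate 0.90, one-sided level 0.05, n = 83. The smallest r with P(X ≥ r | 83, 0.80) ≤ 0.05 is r = 73, with attained level 0.0412. Power is P(X ≥ 73 | 83, 0.90) = 0.7948, which reproduces the stated value of about 80%. Plate type does not enter, so this calculation is untouched by the conflict.

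**2. Can a consecutive series deliver equal numbers?** The documents give no usage shares, so the shares below are assumptions. With one plate type per case, 83/3 = 27.67 and the closest split is 27/28/28. The split of 83 consecutive cases is treated as multinomial. If p is the share of the rarest type, reaching 27 of it takes 27/p cases on average, and 27/p − 83 is the approximate number passed over.

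| Assumed shares (%) | Expected counts in 83 | P(27/28/28, any order) | P(every type 25–31) | Mean cases to reach 27 of rarest | Passed over |
|---|---|---|---|---|---|
| 33.3 each | 27.7 / 27.7 / 27.7 | 2.9% | 30% | – | – |
| 50/30/20 | 41.5 / 24.9 / 16.6 | 0.009% | 0.2% | 27/0.20 = 135 | 52 |
| 60/25/15 | 49.8 / 20.8 / 12.4 | <0.001% | <0.001% | 27/0.15 = 180 | 97 |
| 70/20/10 | 58.1 / 16.6 / 8.3 | <0.001% | <0.001% | 27/0.10 = 270 | 187 |

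Even with equal underlying usage, a roughly even split occurs less than a third of the time. With unequal usage it essentially does not occur unless cases are passed over. Cases carrying two types could narrow the gap.

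**3. What would enforcing the aim do to the pooled rate?** The documents give no healing rates by plate, so these are assumptions too. Usage is taken as 70/20/10%. The rate as used is 0.70a + 0.20b + 0.10c; under equal numbers it is (a + b + c)/3. The chance of meeting 73/83 treats the count as binomial at the pooled rate.

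| Assumed healing by type (%) | Rate as used | Rate at equal numbers | P(≥73/83) as used | P(≥73/83) at equal numbers |
|---|---|---|---|---|
| 95/90/80 | 0.665 + 0.180 + 0.080 = 92.5% | 88.3% | 95.4% | 62.5% |
| 80/90/95 | 0.560 + 0.180 + 0.095 = 83.5% | 88.3% | 17.3% | 62.5% |
| 90/90/90 | 90.0% | 90.0% | 79.5% | 79.5% |

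The shift is downward if the rarest plate heals worst, upward if it heals best, and absent if healing does not differ by plate.

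**The case against.** The strongest reply is that the equal split is only something aimed for. No section sets a per-plate number or a cap, or permits an eligible case to be passed over. Sections 10.5 and 11.1 are the operative rules, and completion (10.11) and sample size (16.1) count 83 cases with no plate split. A site that follows them skips nobody. This stands. A reader might infer that the plan imposes a quota and that cases must be skipped; the text does not support that.

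Second, skipping would leave a trace. Section 11.4.1 puts every 2010–2018 recipient on the screening log. For the identification log, section 11.4.2 says "All patients who meet the inclusion criteria and none of the exclusion criteria must be entered on the log sequentially". Section 12.4.6 requires deviations to be documented and explained, and section 20 prohibits waivers. This stands in part. The logs would show the gap, but whether passing over a case for plate balance is a deviation depends on which instruction governs, and the protocol text does not require such cases to be reported with reasons.

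A reader might also infer three further things, none of which the documents support:

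- *That the tested rate reflects an artificial plate mix.* This needs both enforcement of the aim and healing that differs by plate.
- *That plate types would come from different periods with different follow-up.* This too arises only if cases are skipped, and follow-up runs to the last consultation at one year or later, so an earlier operation does not by itself change it.
- *That 83 not being divisible by three is a fault.* If a case can carry two types, the counts need not sum to 83.

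Nor is low power within each plate type a defect, since no per-plate test is planned.

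**Conclusion.** The conflict is real: two stated instructions cannot in general both be met, the plan does not rank them, and acting on the balance aim would remove the bias safeguard in section 10.7. It should be corrected before case identification begins.

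The conclusion goes no further. Loss of the consecutive series is a risk that depends on how the site reads section 10.3; the documents do not say it will happen. The numbers passed over (about 52 to 187) rest on assumed usage shares and one plate type per case. The size and direction of any change in the pooled healing rate cannot be derived from the documents, and the change is zero if healing does not differ by plate type. The sample size of 83 and its power of 0.795 are unaffected.

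**What to change.** Delete "aiming for an equal number of each" from section 10.3 and the synopsis, or keep it and state that 10.5 and 11.1 prevail and that no eligible case is passed over for plate type. In section 16.2, add a table of the observed plate mix and of healing by plate type with exact 95% limits, giving multi-plate cases their own row.

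The cost is wording and one table; n and power do not change. The downside is that the rarest plate may be thinly represented. At an assumed 10% share, 83 × 0.10 = 8.3, or about 8 cases. Even 8 of 8 healed gives a two-sided exact 95% lower limit of only 0.025^(1/8) = 0.63. This matters because section 7.2 aims to collect data on all implants of the system.

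If the sponsor needs balanced numbers per plate, define in advance a strictly reverse-consecutive sub-series for each type, with a rule for multi-plate cases. Log every case passed over, and describe the series as consecutive within plate type only.
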